10. ENROLLMENT

Potential subjects will be identified by the Investigator or study staff based on patients' clinical and radiographic assessments during regular medical care. The Investigator or study staff will provide study information and the approved Informed Consent Form to all eligible subjects, (determined via Inclusion/Exclusion criteria), as well as answer any questions about the study.

Once the consent form is signed, the subjects will be assigned a unique subject identification number through the EDC system. Once they complete the first set of pre-operative questionnaires, they will be assigned to one of two treatment arms: A) Treatment with the iTotal CR or B) Treatment with an off-the-shelf knee replacement. The site will be instructed to consecutively enroll 10 subjects per treatment arm, alternating between each arm, until enrollment is completed.

The subject identification number will be comprised of a five digit number starting with a two digit site number assigned by ConforMIS at the Site Initiation followed by a three digit subject number, assigned chronologically for the entire study. For example, at site 01, the first subject enrolled will receive number 01-001, followed by 01-002, 01-003, etc.

The Investigator and/or study staff will assess the subject against the Inclusion and Exclusion criteria to determine eligibility. Eligibility includes clinical assessments, radiographic assessments, and a review of the subject's medical history. The radiographic assessments should include:

1. Knee x-ray: 3 views – AP, lateral, sunrise or Merchant
2. Three foot standing x-ray (full length, full weight-bearing film): AP view

If the subject is not eligible to participate in the study, the subject will not be enrolled and is considered a screen failure. All screen failures will be tracked by the site manually in a tracking spreadsheet and electronically in a clinical database. Subject identification numbers for screen failures will not be re-used.

The following Case Report Forms will be completed for all screen failures:

- SUBJECT INFORMATION/MEDICAL HISTORY
- INCUSION/EXCLUSION CRITERIA

If the subject is eligible to participate in the study, they will be assigned to a treatment arm and will be considered enrolled when they are implanted with a device.

11. SCHEDULE OF EVALUATIONS BY VISIT

A table displaying the Schedule of Evaluations is in Appendix A. Regardless of treatment arm assigned, subjects will complete each visit in the schedule of evaluations below.

11.1. **Preoperative Visit (Up to 4 months prior to Surgery)**

Many of the screening assessments required to ensure subject eligibility are also considered the pre-operative assessments. The results of the assessments will be captured on the following Screening/Pre-operative Case Report Forms:

- SUBJECT INFORMATION / MEDICAL HISTORY
- CONCOMITANT MEDICATIONS
- PAIN MEDICATIONS
- INCLUSION/EXCLUSION CRITERIA
- KNEE SOCIETY SCORE (Surgeon portion)

The subject will complete the following function tests and questionnaires to assess pain and function as part of their preoperative assessment:

- THE KNEE INJURY AND OSTEOARTHRITIS OUTCOME SCORE (KOOS)
- KNEE SOCIETY SCORE (Subject portion)
- TIMED "GET UP AND GO"
- 8 METER WALK
- TIMED UP AND DOWN STAIRS

X-rays:

- 3 views – AP, lateral, sunrise or Merchant
- Three foot standing x-ray (full length, full weight-bearing film): AP view

11.2. **Surgery Visit (Day 0)**

The Investigator will surgically implant either the iTotal CR in compliance with the ConforMIS surgical training and Instructions for Use, or the off-the-shelf TKR per their surgical training and the manufacturer's Instructions for Use.

The site will complete the following Case Report Forms:

- SURGICAL SUMMARY
- DISCHARGE SUMMARY
- CONCOMITANT MEDICATIONS (optional)
- PAIN MEDICATIONS
- ADVERSE EVENTS (if any occur during surgery through discharge from hospital)

X-rays: None

11.3. **90 Days Follow-up Visit (\pm 14 days)**

At the 90 days follow-up visit, the Investigator or study staff will perform a post-operative knee assessment and identify any adverse events that have occurred since the subject was discharged from the hospital. The site will also collect the Uniform Billing (UB) form from their billing department if contracted with the Sponsor to participate in the Economic Sub-study.

The site will complete the following Case Report Forms:

- FOLLOW UP
- KNEE SOCIETY SCORE (Surgeon portion)

- CONCOMITANT MEDICATIONS (optional)
- PAIN MEDICATIONS
- ADVERSE EVENTS (if any)
 - REVISION FORM (if necessary)

The subject will complete the following function tests and questionnaires to assess post-operative pain and function:

- THE KNEE INJURY AND OSTEOARTHRITIS OUTCOME SCORE (KOOS)
- KNEE SOCIETY SCORE (Subject portion)
- TIMED “GET UP AND GO”
- 8 METER WALK
- TIMED UP AND DOWN STAIRS

X-rays:

- 3 views – AP, lateral, sunrise or Merchant*
- Three foot standing x-ray (full length, full weight-bearing film): AP view*

**(Depends on hospital standards. Protocol requires only one set of post-op x-rays at either 90 or 180 days)*

11.4. **180 Days Follow-up Visit (± 21 days)**

At the 180 days follow-up visit, the Investigator or study staff will perform knee assessments and identify any adverse events that have occurred since the last visit.

The site will complete the following Case Report Forms:

- FOLLOW UP
- KNEE SOCIETY SCORE (Surgeon portion)
- CONCOMITANT MEDICATIONS (optional)
- PAIN MEDICATIONS
- ADVERSE EVENTS (if any)
 - REVISION FORM (if necessary)

The subject will complete the following function tests and questionnaires to assess post-operative pain and function:

- THE KNEE INJURY AND OSTEOARTHRITIS OUTCOME SCORE (KOOS)
- KNEE SOCIETY SCORE (Subject portion)
- TIMED “GET UP AND GO”
- 8 METER WALK
- TIMED UP AND DOWN STAIRS

X-rays:

- 3 views – AP, lateral, sunrise or Merchant*
- Three foot standing x-ray (full length, full weight-bearing film): AP view*

**(depends on hospital standards. Protocol requires only one set of post-op x-rays at either 90 or 180 days)*

11.5. **Year 1, 2, and 5 Follow-up Visits (± 2 months)**

At the 1 year, 2 year, and 5 year follow-up visits, the Investigator or study staff will perform a knee assessment and identify any adverse events that have occurred since the subject's last visit.

The site will complete the following Case Report Forms:

- FOLLOW UP
- KNEE SOCIETY SCORE (Surgeon portion)
- CONCOMITANT MEDICATIONS (optional)
- PAIN MEDICATIONS
- ADVERSE EVENTS (if any)
 - REVISION FORM (if necessary)

The subject will complete the following function tests and questionnaires to assess post-operative pain and function:

- THE KNEE INJURY AND OSTEOARTHRITIS OUTCOME SCORE (KOOS)
- KNEE SOCIETY SCORE (Subject portion)
- TIMED "GET UP AND GO"
- 8 METER WALK
- TIMED UP AND DOWN STAIRS

X-rays: None

11.6. Year 3, 4, 6, 7, 8, and 9 Follow-up Visits (\pm 3 months)

On the anniversary of the implant surgery for years 3, 4, 6, 7, 8, and 9, the Investigator or study staff will assess the subject for complications or adverse events, and specifically to determine if the iTotal CR or off-the-shelf total knee has been revised. It is not necessary for the subject go to the clinic for a visit, as the site can obtain the data via direct communication with them (such as via telephone or email).

The site will complete the following Case Report Form:

- FOLLOW UP
- ADVERSE EVENTS (if any)
 - REVISION FORM (if necessary)

X-rays: None

11.7. Year 10 Follow-up Visit (\pm 4 months)

On the 10 year anniversary of the implant surgery, the Investigator or study staff will assess the subject to determine if the iTotal CR or off-the-shelf total knee has been revised.

The site will complete the following Case Report Form:

- FOLLOW UP
- KNEE SOCIETY SCORE (Surgeon portion)
- CONCOMITANT MEDICATIONS (optional)
- PAIN MEDICATIONS
- ADVERSE EVENTS (if any)
- REVISION FORM (if necessary)

The subject will be asked to complete the following function tests and questionnaires to assess long term post-operative pain and function. Note that the subject should return to the clinic to complete these questionnaires.

- THE KNEE INJURY AND OSTEOARTHRITIS OUTCOME SCORE (KOOS)
- KNEE SOCIETY SCORE (Subject portion)
- TIMED “GET UP AND GO”
- 8 METER WALK
- TIMED UP AND DOWN STAIRS

X-rays: None

11.8. **Early Termination Visit**

In the event that the study subject ends their participation in the study prior to the 10 year visit, the investigator or designated study staff will complete the following CRFs:

- SUBJECT DISPOSITION
- CONCOMITANT MEDICATIONS (optional)
- PAIN MEDICATIONS
- ADVERSE EVENTS (if any)
 - REVISION FORM (if necessary)

The Investigator or designated study staff will make every attempt to complete the following evaluations:

- THE KNEE INJURY AND OSTEOARTHRITIS OUTCOME SCORE (KOOS)
- KNEE SOCIETY SCORE (Subject and Surgeon portion)
- TIMED “GET UP AND GO”
- 8 METER WALK
- TIMED UP AND DOWN STAIRS

12. SAFETY REPORTING

All Adverse Events (AEs) that are at least possibly related to the knee replacement device or procedure will be recorded by the site from surgery on the Adverse Event CRF and should be reported to Sponsor within 5 working days of site becoming aware of the event. In addition, all Serious Adverse Events (SAEs) and Unanticipated Adverse Device Effects (UADEs) must be reported to ConforMIS or designee via [contact]) or email ([contact]) as soon as possible once discovered by the site. SAEs should be reported to ConforMIS within 3 working days, and UADEs should be reported to ConforMIS within 2 working days. The Investigator and investigative site will also be responsible for required reporting to the site’s Institutional Review Board / Independent Ethics Committee (IRB/IEC) for all AEs, SAEs, and UADEs.

In the communications to ConforMIS or the IRB, include the protocol number and subject ID either in the subject of the email or the beginning of the call. ConforMIS will confirm receipt of the AE/SAE. If possible, include the AE/SAE CRF and supporting documents to ConforMIS as soon as possible.

For the purposes of this protocol, for the first 90 days following surgery, all AEs categorized as Possible, Probable or Definite in relationship to the device or procedure should be

recorded. At day 91, only those AEs categorized as Possible, Probable, or Definite in relationship to the device, as deemed by the investigator, will be recorded. Those events that are Unlikely or Not Related to the device and procedure will not be collected. Please see definitions below.

All SAEs will be recorded regardless of relationship to the device or procedure.

ConforMIS will be responsible for safety reporting as required by applicable regulatory bodies.

Adverse Event: Any untoward or unfavorable medical occurrence associated with the use of a medical product in a human patient, including any abnormal sign, symptom, or disease. Report only those AEs with Possible or above, relationship.

Definite:	Clear-cut temporal association and no other possible cause.
Probable:	Clear-cut temporal association and a potential alternative etiology are not apparent.
Possible:	Temporal association is less clear and other etiologies are also possible.
Unlikely:	Temporal association and the nature of the event is such that the study device is not likely to have had any association with the observed event (cause and effect relationship improbable but not impossible)
Not Related:	There is no temporal association and/or evidence exists that the event is definitely related to another etiology

Serious Adverse Event: Any undesirable experience associated with the use of a medical product in a patient in which the patient outcome is: death, a life-threatening event, inpatient hospitalization or prolongation of existing hospitalization, a persistent or significant disability/incapacity, a congenital anomaly/birth defect or requires intervention to prevent permanent impairment or damage.

Unanticipated Adverse Device Effect (21 CFR 812.3): Any serious adverse effect on health or safety or any life-threatening problem or death caused by, or associated with, a device, if that effect, problem, or death was not previously identified in nature, severity, or degree of incidence in the investigational plan or application (including a supplementary plan or application), instructions for use, informed consent or any other unanticipated serious problem associated with a device that relates to the rights, safety, or welfare of patients.

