7.2. Secondary Endpoints

The study secondary endpoints are:

1. The 2011 Knee Society Knee Scoring System[®] (KSS) and/or its subscales at 1 Year post-implantation
2. The Knee Injury and Osteoarthritis Outcome Score (KOOS)
3. Incidence of major procedure-related and device-related complications, including revision rates
4. Post-operative limb alignment

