- The absolute change from baseline to 1 Year for each subscale of KOOS will be analyzed using an analysis of covariance (ANCOVA) with factor of treatment (iTTotal CR, OTS) and the respective baseline score as a covariate. The least squares means will be presented along with the observed means.
- Post-operative limb alignment will be dichotomized as in and out of “safe zone” (+/- 3 degrees neutral mechanical axis alignment). The proportion of subjects in each study arm summarized and compared using a CMH test.

Safety Analysis

Procedure-related and device-related adverse events (AEs) occurring during the study will be recorded. For the safety population, AEs will be summarized by study arm, the number of subjects reporting AEs, severity, relationship to procedure, relationship to device, and seriousness.

In addition to overall AE summaries, AEs will be summarized for the following study periods:

- Day of procedure to 6 months post procedure
- Annual summaries (1 Year, 2 Year, etc.) from day of procedure

All serious adverse events (SAEs) will be summarized by study arm, severity, relationship to procedure, and relationship to device. SAEs will also be listed by subject.

All information pertaining to AEs noted during the study will be listed by subject.

The Fisher’s Exact test will be used to compare the proportion of subjects in each study arm who have the following:

- procedure-related AEs
- device-related AEs
- revision procedures

Missing Efficacy Data Imputation

The last observation carried forward (LOCF) method will be used to impute missing efficacy data.

Sample Size Determination

A total sample size of a minimum of 450 and a maximum of 600 subjects will be prospectively enrolled in a consecutive fashion, to each arm of the study (approximately 225-300 in the iTotal CR arm and 225-300 in the OTS arm). To ensure that enrollment in each arm remains relatively even, sites assigned odd site numbers will begin by enrolling off-the-shelf subjects and even numbered sites will begin by enrolling ConforMIS subjects. Based on data from a previous study, it is expected that a minimum of 450 and a maximum of 600 total subjects will provide greater than 80% power for the primary functional endpoint.

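### From day 91, non-serious AEs judged related to the procedure but not the device go unrecorded, so procedure-related AE summaries and the Fisher test may be incomplete beyond day 90

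*Combined protocol and SAP*

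**What the plan says.** **Collection (Section 12, Safety Reporting).** The section opens with a general rule: AEs "that are at least possibly related to the knee replacement device or procedure will be recorded by the site from surgery". No end date is given. It then sets two windows. In the first, "for the first 90 days following surgery, all AEs categorized as Possible, Probable or Definite in relationship to the device or procedure should be" recorded. In the second, "At day 91, only those AEs categorized as Possible, Probable, or Definite in relationship to the device", on the investigator's judgement, are recorded. The next sentence excludes events graded Unlikely or Not Related to the device and procedure. A separate sentence has every SAE recorded whatever its relationship, without a time limit.

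**Analysis (Section 15, Safety Analysis).** The premise is that "Procedure-related and device-related adverse events (AEs) occurring during the study will be recorded". AEs are summarised by arm, including by relationship to procedure and, separately, by relationship to device. Besides overall summaries, the periods are "Day of procedure to 6 months post procedure" and "Annual summaries (1 Year, 2 Year, etc.) from day of procedure". Fisher's exact test compares the arms on the proportion of subjects with procedure-related AEs, with device-related AEs and with revision procedures. No time window is attached to the test.

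**Endpoint (Section 7.2).** Secondary endpoint 3 is "Incidence of major procedure-related and device-related complications, including revision rates". The term *major* is not defined.

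**Follow-up and blinding.** Follow-up runs to 10 years (Section 6), and a revision form is available at every follow-up contact (Sections 11.3 to 11.7). The only person stated to be blinded is the one who administers the functional tests (Section 3). The investigator implants the device (Section 11.2).

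**The concern.** The collection rule and the analysis plan do not describe the same data. If sites follow the day-91 sentence, a 1 Year or 2 Year figure for procedure-related AEs carries a label that its collection rule does not support. For non-serious events attributed only to the procedure, it is a 90-day figure. If some sites follow the opening sentence of Section 12 instead, capture differs between sites for reasons unrelated to the implants.

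Attribution also takes on a second role. Up to day 90 it only classifies a related event. From day 91 the investigator's judgement of device against procedure decides whether a non-serious event enters the database at all. Section 12 gives no criteria for separating the two, and the investigator is not stated to be blinded. An event left out in this way cannot be re-adjudicated later, because no record of it exists.

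**Working it through.** **1. What is still recorded after day 90**

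| Event after day 90 | Day-91 sentence, with the SAE sentence | Opening sentence of Section 12 |
|---|---|---|
| SAE, any relationship | recorded | recorded if related (all SAEs by the SAE sentence) |
| Non-serious, at least possibly device-related, whether or not also procedure-related | recorded | recorded |
| Revision | recorded on its own form to year 10 | same |
| Non-serious, procedure-related, less than possibly device-related | **not recorded** | **recorded** |

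The conflict is confined to the last row, called *procedure-only* below.

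**2. Which planned results use that row**

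- AE summaries by relationship to procedure, to 6 months and for each year: yes.
- Fisher's exact test on subjects with procedure-related AEs: yes, since no window limits it to day 90.
- Secondary endpoint 3: only for a late event that is major, non-serious, procedure-only and not a revision.
- Revision comparison: no.
- Device-related AE comparison: only through how investigators attribute events.

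**3. Share of each window in which procedure-only, non-serious AEs are collected**

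Inputs: 90 days (Section 12); summary periods (Section 15); 10 years (Section 6). Share = 90 / window length in days.

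- 6 months: 90/183 = 49%
- 1 year: 90/365 = 25%
- 2 years: 90/730 = 12%
- 5 years: 90/1826 = 5%
- 10 years: 90/3652 = 2.5%

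These are shares of calendar time. They would equal shares of events only if such events occurred at a constant rate, which nothing in the documents supports.

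**4. Illustration of what a loss could do**

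The documents give no AE rate, timing, serious share, or power for this comparison, so there is no planned figure to reproduce. All of the following are assumptions except the arm size of 225 (Section 15): true proportions p₁ = 20% and p₂ = 10%; two-sided alpha 0.05; a normal approximation in place of Fisher's test; equal loss in both arms.

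Let f be the fraction of affected subjects whose only procedure-related AEs fall after day 90, and s the share of those whose events are all non-serious and procedure-only. The lost fraction is L = f × s, and the recorded proportion is p(1 − L).

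Power = Φ{[(p₁ − p₂) − 1.96 √(2p̄(1 − p̄)/n)] / √[(p₁(1 − p₁) + p₂(1 − p₂))/n]}, where p̄ is the mean of the two proportions.

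| f | s | L | Recorded proportions | Power |
|---|---|---|---|---|
| none lost | – | 0 | 20.0% vs 10.0% | 84.6% |
| 5% | 50% | 0.025 | 19.5% vs 9.75% | 83.5% |
| 10% | 50% | 0.05 | 19.0% vs 9.5% | 82.4% |
| 10% | 90% | 0.09 | 18.2% vs 9.1% | 80.5% |
| 40% | 90% | 0.36 | 12.8% vs 6.4% | 63.5% |

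The effect runs from about 1 percentage point of power to about 21, depending wholly on f and s. With equal loss the ratio of the two proportions stays at 2, while the absolute difference shrinks from 10 points to between 9.75 and 6.4.

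**The case against.** The best reply is that Section 12 sets a specific collection window for this protocol and Section 15 speaks in general terms subject to it. The period summaries in Section 15 are of AEs overall, not of procedure-related AEs in particular. The events that matter most after day 90 remain captured as SAEs, as revisions, or because they clear the low bar of being possibly device-related. The exclusion sentence, read literally, removes only events unrelated to both device and procedure, so sites may go on recording late procedure-related events. The comparison is an unpowered safety analysis.

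Much of this stands, and it rules out several stronger readings that a reader might infer:

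- *All procedure-related AEs stop at day 91.* They do not. Step 1 shows that one class is lost.
- *Secondary endpoint 3 is cut off at 90 days.* It covers major complications, many of which may meet the SAE definition or be revisions. The undefined term leaves a gap but does not show a loss.
- *Half of the 6-month events, or three quarters of the year-1 events, are missing.* The percentages refer to time. Procedure-related events may well cluster early.
- *The comparison is biased towards one arm.* The rule is the same in both arms, and relationship to device and to procedure are summarised as separate attributes. Calling an event procedure-related does not by itself remove it; it must also be judged less than possibly device-related. Differential loss is possible but not shown.

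What the reply does not do is settle the text. Section 15 does summarise by relationship to procedure, its Fisher test has no window, and no sentence says that either stops at day 90. The literal reading of the exclusion sentence adds a further route to uneven recording.

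**Conclusion.** The inconsistency is in the current text and is narrow. From day 91, non-serious procedure-only AEs are not recorded under one sentence of Section 12, while the opening of that section and Section 15 treat them as recorded. The 6-month and annual summaries by relationship to procedure, and the Fisher test on procedure-related AEs, may therefore be incomplete after day 90 without saying so.

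The size in events is unknown and cannot be obtained from the documents; in time, the class is covered for about 49% of the 6-month window and 25% of year 1. This conclusion assumes that sites apply the day-91 sentence as written. If they do not, the problem becomes uneven capture between sites. The primary functional endpoint is unaffected. The sponsor should correct this, because it determines what the trial may say about procedure-related safety beyond three months.

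**What to change.** Reconcile Sections 12 and 15 before analysis, in one of two ways:

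- **(a) Align collection with the analysis.** Drop the day-91 restriction so that AEs at least possibly related to the procedure are recorded throughout. The cost is modest extra AE form work. For subjects already past day 90 when the change takes effect, events left unrecorded may not be recoverable.
- **(b) Align the analysis with collection.** Define the procedure-related AE summaries and the Fisher test as Day 0 to Day 90, label later periods as device-related AEs and all SAEs, and bring the opening sentence of Section 12 and the premise in Section 15 into line. This costs wording only.

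In either case, define *major* in Section 7.2, so that it is clear whether secondary endpoint 3 can include non-serious events and over what period.

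A combined comparison of device- or procedure-related AEs would be a useful supplement, because moving an event from one label to the other would not change it. That protection holds throughout follow-up only under (a). Under (b) it holds only to day 90, since pooling cannot restore events that were never collected.

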3. STUDY DESIGN

This is a prospective, blinded, multi-center study that will be conducted in the US, UK, and Germany. The study will include a minimum of 450 and a maximum of 600 subjects across up to 20 sites with up to 225 min- 300 max subjects in the iTotal CR arm and 225 min- 300 max subjects in the off-the-shelf total knee arm. An additional 25% may be enrolled to account for subject discontinuation.

Subjects will be consecutively recruited in groups of 10, alternating between study arms until enrollment is completed. Once a series of 10 is recruited (subject signed consent and completed pre-op questionnaires), then the next series of 10 is to be recruited.

To ensure that enrollment in each arm remains relatively even, sites assigned odd site numbers will begin by enrolling off-the-shelf subjects and even numbered sites will begin by enrolling ConforMIS subjects. Subjects will be implanted with either an iTotal CR or an off-the-shelf cruciate retaining total knee replacement.

The person administering the functional tests will be blinded. The blind will be maintained for at least one year in order to maintain an objective assessment of each patient's function. Investigators and study staff will make every attempt to maintain the blind by limiting access to study data, x-rays, and other evaluations.

For all surgeries, the preferred surgical approach is to make an incision that is midline or slightly medial to midline, followed by a parapatellar arthrotomy, or a subvastus arthrotomy with prior written approval from Sponsor. The surgeon must use the same approach for all study subjects.

For surgical technique, the off-the-shelf goal is to obtain mechanical alignment.

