5.0 AD	27 March 2017	[name]	
Updated the title from: “A Prospective, Randomized, Multicenter Study to Evaluate the ConforMIS iTotal (CR) Knee Replacement System versus Off-the-Shelf Replacement” to “A Prospective, Multicenter Study to Evaluate Functional Outcome After Knee Replacement”
 
Throughout document, oxford comma used
 
Updated ConforMIS address
 
Added ConforMIS internal use ID
 
Deleted randomization throughout the protocol
 
Deleted the use of patient specific instrumentation.
 
Updated the study design to reflect no randomization.
 
Deleted double blinding. Only functional tester is blinded. Updated throughout protocol.
 
Updated N

		
Updated language for economic study. Only sites who are contracted with ConforMIS will take part.
 
Updated timed “Get-up and Go” test definition to clarify the length of the walk.
 
Updated 8 meter walk with the correct reference. National Institutes of Health instead of McCarthy.
 
Updated the Timed Up and Down Stairs Test to include a minimum of 4 steps in a flight of stairs.
 
Deleted the patient reported outcomes as a primary endpoint.
 
Added KSS as a secondary endpoint. Updated statistical analyses with KSS information.
 
Updated exclusion criteria to provide clarity. Deleted “Other lower extremity surgery within 1 year” to “Lower extremity surgery (orthopaedic or ligament injury) on either limb to the hip, ankle, feet occurring or expected to occur within 1 year of surgery on the evaluated knee”
 
Updated exclusion criteria to provide clarity. Changed “Contralateral knee replacement surgery within the past 6 months” to “Contralateral knee replacement occurring or expected to occur within 6 months of surgery on the evaluated knee”
 
Added instructions on how a site will consecutively enroll subjects.
 
Administrative changes to provide clarity.
 
Clarified Safety reporting. Added phone number and email along with instructions of what needs to be included in the communications to the sponsor and the IRB.
 
Updated efficacy analysis

--	--	---

			Updated the sample size determination paragraph Updated Appendix A to reflect changes
--	--	--	--

20. APPENDIX A – Schedule of Evaluations

Evaluation	Screening/ Pre-Op	Surgery	90 Days Follow-up	180 Days Follow-up	Year 1, 2, 5 Follow-up	Year 3, 4, 6, 7, 8, 9 Follow-up	Year 10 Follow-up

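### Non-serious adverse events are collected only if an investigator who knows the arm rates them related, so two of the three Fisher safety comparisons rest on unblinded attribution

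*Combined protocol and SAP*

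**What the plan says.** **Collection (Section 12).** AEs "at least possibly related to the knee replacement device or procedure will be recorded by the site from surgery". A later paragraph limits this: through day 90, events at least possibly related to the device or the procedure are recorded, and from day 91 "only those AEs categorized as Possible, Probable, or Definite in relationship to the device, as deemed by the investigator, will be recorded". On everything below that threshold: "Those events that are Unlikely or Not Related to the device and procedure will not be collected". SAEs are exempt: "All SAEs will be recorded regardless of relationship to the device or procedure".

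**Definitions (Section 12).** Not Related reads: "There is no temporal association and/or evidence exists that the event is definitely related to another etiology". Possible, which is a recorded category, covers a less clear temporal link with other causes also possible. Unlikely is worded for the study device only.

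**Blinding (Section 3).** "The person administering the functional tests will be blinded". The version 5.0 entry in the protocol history agrees with the current text: "Only functional tester is blinded". Under Section 11.2 the investigator implants the device.

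**Analysis (Section 15, Safety Analysis).** Fisher's exact test "will be used to compare the proportion of subjects in each study arm who have the following": procedure-related AEs, device-related AEs and revision procedures. SAEs are summarised by arm and listed, and no test is named for them. Related complications, including revisions, are a secondary endpoint (Section 7.2).

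**The concern.** Relatedness is usually a descriptor attached to a recorded event. Here, for non-serious events, it decides whether a record exists at all. The person deciding has implanted the device and knows which one it was. If investigators attribute similar complaints differently in the two arms, the related-AE comparisons measure attribution as well as harm. The effect could go either way: a difference could appear where none exists, or a real one could be hidden.

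Because the filter acts at collection, analysis cannot repair it. Events that were never entered cannot be re-rated, adjudicated or put into a sensitivity analysis. The exposed group is non-serious events of the operated knee that do not lead to revision. The study follows subjects for 10 years, and for most of that time only device-related non-serious events are kept.

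**Working it through.** **1. Does the rater know the arm?** Section 11.2 has the investigator implant the device. Section 3 blinds only the functional tester; its instruction to limit access to data and x-rays protects that blind. The oversight committee in Section 9 reviews site performance and data integrity. No blinded or independent review of relatedness appears anywhere. So yes.

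**2. Which safety outcomes pass through the filter?**

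| Outcome | Filtered by relatedness at collection? | Between-arm test in Section 15? |
|---|---|---|
| Procedure-related AEs | Yes, for non-serious events | Fisher |
| Device-related AEs | Yes, for non-serious events | Fisher |
| Revision procedures | No | Fisher |
| All SAEs | No | None named; summarised by arm |

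Two of the three tested outcomes are filtered. The broad event category collected without the filter has no test.

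**3. Do the definitions exclude late events?** The and/or in Not Related makes lack of temporal association sufficient by itself, so a late knee complaint may be excluded on timing alone. But Possible also fits such a complaint, and it is recorded. The wording permits the exclusion and does not require it.

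**4. Is Section 12 consistent with itself and with Section 15?** The opening sentence of Section 12 covers device or procedure from surgery, with no time limit. The day-91 rule drops non-serious events related only to the procedure. Section 15 nevertheless plans a procedure-related AE test and annual AE summaries counted from the day of the procedure. These do not agree.

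**5. How large could the effect be?** The documents give no AE rate, safety alpha or safety power, so there is no stated figure to reproduce. What follows is an illustration.

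- From Section 15: n = 225 to 300 per arm.
- Assumed: true proportion of subjects with a non-serious knee AE, p = 20% in both arms; probability a of being called related, by arm; at most one event per subject; two-sided alpha 0.05.
- Recorded rate = p × a.
- Rejection probability = Σᵢ Σⱼ Bin(i; n, r₁) · Bin(j; n, r₂) · 1{Fisher p ≤ 0.05}, where r₁ and r₂ are the recorded rates, summed exactly over both binomials.

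| Attribution | Recorded rates | Rejects, 225/arm | Rejects, 300/arm |
|---|---|---|---|
| 80% vs 80% | 0.20 × 0.80 = 16% in both | 3.7% | 3.9% |
| 60% vs 80% | 0.20 × 0.60 = 12% vs 16% | 19.3% | 25.4% |
| 50% vs 80% | 0.20 × 0.50 = 10% vs 16% | 42.3% | 54.5% |

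At 225 per arm, 45 subjects in each arm have an event (225 × 0.20). With 60% vs 80% attribution, 27 and 36 are recorded, so 18 and 9 are lost.

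Masking works the same way. Take a true 10% vs 20% difference:

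| Attribution (low-rate arm, high-rate arm) | Recorded rates | Power, 225/arm | Power, 300/arm |
|---|---|---|---|
| No filter | 10% vs 20% | 82% | 92% |
| 90%, 90% | 9% vs 18% | 77% | 88% |
| 90%, 60% | 9% vs 12% | 14% | 19% |

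An equal filter costs some power and does not inflate the error rate. Only attribution that differs by arm does the damage.

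**The case against.** The strongest case for the plan has five parts.

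- **Serious harm is largely captured.** A reader might infer that only filtered counts are compared between arms. Section 15 does not support that. Revisions are tested with no relatedness qualifier, and revision status is actively checked in both arms at the remote contacts in years 3, 4 and 6 to 9 and again at year 10. The SAE definition includes hospitalisation, lasting disability and intervention to prevent permanent impairment, so many late failures are recorded without the filter. This stands, and it confines the point to non-serious, unrevised events.
- **Late events have a recorded category.** A reader might infer that the definitions push late implant events into Not Related. They do not: Possible fits such events, Section 12 keeps device-related AEs recordable after day 90, and yearly contacts ask about complications. This stands; the wording is permissive only.
- **Surgical events are not lost early on.** A reader might infer that, because Unlikely mentions only the device, a purely surgical event is dropped. In the first 90 days relation to either device or procedure suffices, so an event Unlikely for the device but Possible for the procedure is recorded. The narrow wording of Unlikely leaves only an ambiguity about procedure events and the off-the-shelf arm.
- **Testing related events matches the declared endpoint.** Section 7.2 names related complications, and all-cause SAEs over 10 years include events that have nothing to do with the knee. This is fair. The all-cause comparison should sit beside the related-event tests and not replace them.
- **The bias is hypothetical.** Every site enrols both arms in alternating groups of ten, so differences in rating threshold between sites touch both arms. Only arm-specific rating creates bias, and the documents hold no evidence of it. This stands as a limit on size. It does not supply a safeguard, because the filter leaves no unfiltered non-serious data against which to check.

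**Conclusion.** The point holds in a limited form. Collection of non-serious AEs, and with it two of the three Fisher safety comparisons, depends on relatedness as judged by an investigator who knows the arm. No adjudication is described, and excluded events cannot be recovered.

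The size is conditional. With an assumed 20% true rate in both arms and 60% vs 80% attribution, the false-positive rate is about 19% to 25% across the planned arm sizes, against about 4% with equal attribution. At 50% vs 80% it is about 42% to 55%. The true rate, the attribution splits and alpha 0.05 are all assumptions. The documents give neither the size nor the direction of any difference in attribution, so they do not support saying that the comparison is in fact biased or that it favours one device.

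The conflict between the opening rule of Section 12, the day-91 rule and Section 15 is in the text itself and needs no assumption. Safety is not the primary objective, so this does not undermine the main analysis. It should still be amended, because what is not collected now cannot be added later.

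**What to change.** 1. **Section 15:** add a between-arm comparison of the proportion of subjects with any SAE, regardless of relatedness. The data are already collected, so the cost is one extra test.
2. **Section 12, with a matching line in Section 15:** record all AEs of the operated knee or limb through year 10 whatever their rated relatedness. Keep relatedness as a descriptor, and compare these all-cause operated-limb AEs between arms beside the related-AE tests. The cost is a modest number of extra AE forms. This does not blind the reporting itself, but inclusion no longer turns on the relatedness rating, and later re-rating becomes possible.
3. **Section 12 definitions:** state that time since implantation alone does not make an event Not Related. Keep a definite other etiology as sufficient by itself. Simply replacing and/or with and would leave events that are close to surgery but clearly due to another cause without a fitting category. Word Unlikely for the implanted device in either arm or the procedure. This is a wording change only.
4. **Sections 12 and 15:** reconcile the opening sentence of Section 12 (device or procedure, from surgery) with the day-91 device-only rule, and both with the planned procedure-related AE test and annual summaries. State the time period to which the procedure-related comparison applies. This can go into the same amendment.
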